## 9.5. Appendix 5: Reporting Standards for Missing Data

### 9.5.1. Premature Withdrawals

Element	Reporting Detail
General	All available data from subjects in the Safety population who withdrew from mepolizumab will be listed and all available planned data will be included in summary tables and figures, unless otherwise specified.

### 9.5.2. Handling of Missing Data

Element	Reporting Detail
General	
 
Missing data occurs when any requested data is not provided, leading to blank fields on the collection instrument : 
 
These data will be indicated by the use of a "blank" in subject listing displays. Unless all data for a specific visit are missing in which case the data is excluded from the table.
 
Answers such as "Not applicable" and "Not evaluable" are not considered to be missing data and should be displayed as such.
 
 
 

#### 9.5.2.1. Handling of Missing and Partial Dates

Element	Reporting Detail
Adverse Events	
 
Completely missing start or end dates will remain missing, with no imputation applied. Consequently, time to onset and duration of such events will be missing.
 
The eCRF allows for the possibility of partial dates (i.e., only month and year) to be recorded for AE start and end dates; that is, the day of the month may be missing. In such a case, the following conventions will be applied for calculating the time to onset and the duration of the event: 
 
Missing Start Day: First of the month will be used unless this is before the start date of study treatment; in this case the study treatment start date will be used and hence the event is considered On-treatment as per Appendix 2: Treatment States and Phases.
 
Missing Stop Day: Last day of the month will be used, unless this is after the stop date of study treatment; in this case the study treatment stop date will be used.
 
 
 
The recorded partial date will be displayed in listings.
 

Concomitant medications	
 
Partial dates for any concomitant medications recorded in the CRF will be imputed using the following convention: 
 
If the partial date is a start date, a '01' will be used for the day and 'Jan' will be used for the month
 
If the partial date is a stop date, a '28/29/30/31' will be used for the day (dependent on the month and year) and 'Dec' will be used for the month.
 
 
 
The recorded partial date will be displayed in listings.
 

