### 7.1. Adverse Events

Adverse events will be coded using the Medical Dictionary for Regulatory Activities (MedDRA) coding dictionary. Classification of an AE as pre-, on- or post-treatment will be made with reference to the study treatment start and stop date/time and the AE onset date/time. If the AE onset date is missing or partial then the AE will be considered on-treatment unless there is evidence to the contrary (e.g. the month of the onset date is present and is less than the month of the first dose of study medication). AEs with onset up to 4 weeks after the last dose of treatment will be considered on-treatment. AEs with onset after this period will be considered post-treatment but will be assigned to the treatment previously received.

Any SAEs for screen failures, run-in failures or subjects who were enrolled but did not receive treatment will be classified as pre-treatment SAEs.

The most frequent on-treatment AEs will be defined as AEs with frequency  $\geq 3\%$  in any treatment group.

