## 9.2. Appendix 2: Study Phases and Treatment Emergent Adverse Events

### 9.2.1. Study Phases

Treatment State	Definition
Pre-Treatment	AE Start Date/Time < Study Treatment Start Date/Time
On-Treatment	Study Treatment Start Date/Time $\leq$ AE Start Date/Time $\leq$ Study Treatment Stop Date + 28 days
Post-Treatment	AE Start Date > Study Treatment Stop Date + 28 days

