### 9.4.2. Study Population

Extent of Exposure

 
Number of days of exposure to study drug will be calculated based on the formula:  Duration of Exposure in Days = Treatment Stop Date – (Treatment Start Date) + 29 
 
Participants who were randomized but did not report a treatment start date will be categorised as having zero days of exposure.
 
If there are any treatment breaks during the study, exposure data will be adjusted accordingly.
 

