### 9.4.3. Safety

Adverse Events
Drug Related AEs
AEs with relationship marked 'YES'.
AEs Leading to Permanent Discontinuation from Study Treatment or Withdrawal from the Study
AEs with action marked "Study treatment withdrawn" or withdrawn from study status marked "YES", or a response to either of these questions is missing.
AEs on Day of Dosing
AEs with an onset date equal to a study treatment dosing date and an onset time on or after the study treatment dosing time.
AE Time Since First Dose

 
If AE onset time is missing, calculate in days as follows:-           
 
If AE start date < Date of first dose of study treatment then  <math display="block">\text{Time since first dose} = \text{AE start date} - \text{Date of first dose of study treatment}</math> 
 
If AE start date ≥ Date of first dose of study treatment then  <math display="block">\text{Time since first dose} = \text{AE start date} - \text{Date of first dose of study treatment} + 1</math> 
 
Missing if AE start date or date of first dose of study treatment is missing.
 
 
 
If AE onset time is present, calculate in days, hours, minutes as  <math display="block">\text{Time since first dose} = \text{AE start date/time} - \text{Date/time of first dose of study treatment}</math> 
 

AE Duration (Days)

• If AE onset time is missing, calculate in days as AE end date – AE start date + 1

• If AE onset time is present, calculate in days, hours and minutes as AE end date/time – AE start date/time

• Missing if AE start date or end date is missing.

AEs of Special Interest

• See Section 7.2.

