Serious and Other Significant Adverse Events					
3.10.	Safety	AE1	Summary of Pre-Treatment Serious Adverse Events by System Organ Class and Preferred Term	
 
MEA116841
 
201607For studies with few events/participants listing is sufficient: discuss this option with your disclosure representative.
 
MEA116841 + 201607
 
	IA , SAC

Safety: Tables					
No.	Population	IDSL / Example Shell	Title	Programming Notes	Deliverable [Priority]
3.11.	Safety	AE1	Summary of On-Treatment Serious Adverse Events by System Organ Class and Preferred Term	
 
MEA116841
 
201607For studies with few events/participants listing is sufficient: discuss this option with your disclosure representative.
 
MEA116841 + 201607
 
	IA , SAC
3.12.	Safety	AE1	Summary of Post-Treatment Serious Adverse Events by System Organ Class and Preferred Term	
 
MEA116841
 
201607For studies with few events/participants listing is sufficient: discuss this option with your disclosure representative.
 
MEA116841 + 201607
 
	IA , SAC
3.13.	Safety	AE16	Summary of Serious Adverse Events by System Organ Class and Preferred Term (Number of Participants and Occurrences)	Required for data disclosure 
 
MEA116841
 
201607For studies with few events/participants listing is sufficient: discuss this option with your disclosure representative.
 
MEA116841 + 201607
 
	IA , SAC

Safety: Tables					
No.	Population	IDSL / Example Shell	Title	Programming Notes	Deliverable [Priority]
3.14.	Safety	AE1	Summary of On-Treatment Non-Fatal Serious Adverse Events by System Organ Class and Preferred Term	
 
MEA116841
 
201607For studies with few events/participants listing is sufficient: discuss this option with your disclosure representative.
 
MEA116841 + 201607
 
	IA , SAC
3.15.	Safety	AE1	Summary of Fatal Serious Adverse Events by System Organ Class and Preferred Term	
 
MEA116841
 
201607For studies with few events/participants listing is sufficient: discuss this option with your disclosure representative.
 
MEA116841 + 201607
 
	IA , SAC

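### SAP 9.5.2.1 can turn a partial-date AE from before the first dose into an on-treatment AE, and its end-date cap gives zero, negative or truncated durations

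*SAP*

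**What the plan says.** **Start dates.** SAP 9.5.2.1 sets conventions for AE dates with a missing day, to be used in deriving time to onset and duration. A missing start day becomes the first of the month. If that is before treatment start, "in this case the study treatment start date will be used and hence the event is considered On-treatment". SAP 7.1 also covers partial onset dates: such an AE is on-treatment unless something shows otherwise, and its example is that "the month of the onset date is present and is less than the month of the first dose of study medication".

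**End dates.** For a missing stop day, 9.5.2.1 says "Last day of the month will be used, unless this is after the stop date of study treatment", in which case the treatment stop date is used instead.

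**AEs after treatment.** SAP 7.1 states that "AEs with onset up to 4 weeks after the last dose of treatment will be considered on-treatment". SAP 9.2.1 defines post-treatment as "AE Start Date > Study Treatment Stop Date + 28 days". Table 3.4 summarises post-treatment AEs, and Protocol 5.3 requires a visit 12 weeks after the last dose.

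**Derivations.** For duration, SAP 9.4.3 says "If AE onset time is missing, calculate in days as AE end date – AE start date + 1". Exposure in SAP 9.4.2 is "Duration of Exposure in Days = Treatment Stop Date – (Treatment Start Date) + 29".

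**The concern.** The start rule fires for every recorded month whose first day precedes treatment start. That covers the month of first dose, where it agrees with SAP 7.1, but also all earlier months, where it contradicts 7.1. It also takes no account of a recorded AE end date before the first dose. A pre-treatment SAE could therefore leave Table 3.10 ("Summary of Pre-Treatment Serious Adverse Events by System Organ Class and Preferred Term") for the on-treatment Table 3.11, and with it the exposure-adjusted Table 3.46, with a false onset on day 1.

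The end rule treats treatment stop as the latest possible end of an AE. The plan collects and classifies AEs that start or continue after that date, so their imputed end can precede their start, or the event can be cut short. A negative duration shows itself; a truncated one looks plausible.

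**Working it through.** The plan states no figure on this point, so the check applies its rules literally.

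**Rules used**

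- Imputed start (9.5.2.1): the first of the recorded month, or the first-dose date if that is later.
- Imputed end (9.5.2.1): the last day of the recorded month, or the treatment stop date if that is earlier.
- Duration (9.4.3, no onset time): end - start + 1.
- Treatment stop is read as the date of last dose. This is an inference: 7.1 counts 4 weeks from the last dose where 9.2.1 counts 28 days from the stop date, and the exposure formula adds 29.

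**Assumed dates (illustrative):** first dose 20-Mar-2016, last dose 10-Mar-2019.

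**Start rule**

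- Onset Feb 2016, end Feb 2016. 1 February precedes 20 March, so the start becomes 20-Mar-2016, on-treatment. The end becomes 29-Feb-2016, which is 20 days earlier. Duration = -20 + 1 = -19 days. Section 7.1 treats this onset month as evidence against on-treatment.
- Onset Mar 2016, end 10-Mar-2016 (complete). The start becomes 20-Mar-2016, on-treatment. Duration = 10 - 20 + 1 = -9 days, although the AE ended before the first dose.

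**End rule, general form.** Let an AE have a complete start date k days after treatment stop (k of 1 or more) and a partial end date. The end of the recorded month cannot precede the onset, so it is after treatment stop and the cap always applies. Duration = stop - (stop + k) + 1 = 1 - k days:

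| k (days after stop) | 1 | 14 | 28 | 84 |
|---|---|---|---|---|
| Duration (days) | 0 | -13 | -27 | -83 |

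An AE at k = 28 is still on-treatment; k = 84 is the 12-week visit. This result holds whatever treatment stop is taken to mean.

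**All worked cases.** The last column applies the rule proposed below, with last contact assumed at last dose + 84 days = 02-Jun-2019.

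| Recorded start | Recorded end | Plan (days) | Proposed rule (days) |
|---|---|---|---|
| Feb 2016 | Feb 2016 | -19, on-treatment | 29, pre-treatment |
| Mar 2016 | 10-Mar-2016 | -9, on-treatment | 10, pre-treatment |
| 25-Mar-2019 | Apr 2019 | 10 Mar - 25 Mar + 1 = -14 | 37 |
| 02-May-2019 | May 2019 | -53 + 1 = -52 | 30 |
| 20-Feb-2019 | May 2019 | 18 + 1 = 19 | 101 |
| Mar 2019 | Mar 2019 | 10 - 1 + 1 = 10 | 31 |

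The last two rows show that the cap does not always give a negative value; it can simply shorten the event.

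**The case against.** Six arguments can be made for leaving the text alone.

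- *Section 7.1 sets phase; 9.5.2.1 serves only time to onset and duration.* Its introduction says so, but the sentence itself assigns the on-treatment label and refers to the study-phase appendix, so the sections conflict. Even on the narrow reading, the false day-1 onset and the -19 days remain.
- *An AE that ended before the first dose is contrary evidence under 7.1, whose example is not exhaustive.* That is fair for phase. The derived onset and duration stay wrong.
- *Almost no events are affected.* This largely stands for the start rule. Under Protocol 7.3.1.1, before the first dose only SAEs related to study participation or a sponsor product are required, and SAEs are reported within 24 hours, so a missing onset day should be rare. The documents do not allow a count.
- *The proposed-rule durations are not true values.* Correct. They are the longest that the recorded months allow: 25-Mar-2019 to Apr 2019 could be 8 to 37 days, and 20-Feb-2019 to May 2019 could be 71 to 101. With a screening period of up to 4 weeks, consent for a first dose on 20-Mar-2016 would be no earlier than 21-Feb-2016, so an AE arising after consent could last at most 9 days in February, not 29. These figures follow from the plan's own first-of-month and end-of-month convention. They do not make -14, -19 or 19 days right.
- *The 1 - k formula is not universal.* Where onset time is recorded, 9.4.3 subtracts date/times without adding a day, so the result is about -k. That is still impossible.
- *The impact is small.* The study has no hypotheses, no visible display title names AE duration, and listings keep the recorded partial date, so errors could be traced. This limits the weight of the point. But the SAP defines these derivations and intends to make them.

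**Conclusion.** The concern holds for both rules. As written, 9.5.2.1 contradicts 7.1 for a partial onset month before the first-dose month and can label a pre-dose event on-treatment. Its end-date cap gives 0 days for an onset one day after treatment stop, a negative duration from two days after, and a truncated duration for an event that spans treatment stop.

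The practical size is modest. Only partial dates are involved. The start rule can move an SAE between Tables 3.10 and 3.11, probably rarely; the cap leaves phase, event counts and exposure unchanged. The conclusion rests on the literal text of 9.5.2.1. The worked dates are assumptions, and reading treatment stop as last dose is an inference, but the 1 - k result does not depend on either. The rules should be corrected because they govern both interim and final reporting.

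**What to change.** Amend SAP 9.5.2.1 as follows.

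- **Missing start day:** use the first of the month. Substitute the first-dose date only when the onset month and year equal those of the first dose and no recorded AE end (full date, or month if partial) precedes the first dose. If the onset month is earlier, or the AE ended before the first dose, keep the first of the month and classify the event as pre-treatment, in line with 7.1. Later onset months follow 9.2.1.
- **Missing stop day:** use the last day of the recorded month, capped only at last contact or study end, death or data cut-off, and never earlier than the AE start date.
- **Definition:** state that the treatment stop date is the date of last dose, if that is what is meant.

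The cost is a few sentences and a small programming change. No new data are needed.

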## 9.6. Appendix 6: Abbreviations & Trade Marks

### 9.6.1. Abbreviations

Abbreviation	Description
ADaM	Analysis Data Model
AE	Adverse Event
AESI	Adverse Event of Special Interest
A&R	Analysis and Reporting
CDISC	Clinical Data Interchange Standards Consortium
CS	Clinical Statistics
CSR	Clinical Study Report
CTR	Clinical Trial Register
CVT	Cardiac, Vascular and Thromboembolic
DOB	Date of Birth
DP	Decimal Places
eCRF	Electronic Case Record Form
EGPA	Eosinophilic Granulomatosis with Polyangiitis
FCBP	Female of Childbearing Potential
IA	Interim Analysis
ICH	International Conference on Harmonisation
IDMC	Independent Data Monitoring Committee
IDSL	Integrated Data Standards Library
IP	Investigational Product
GSK	Glaxo SmithKline
GUI	Guidance
LAP	Long-term Access Programme
LOC	Last Observation Carries Forward
MedDRA	Medical Dictionary for Regulatory Activities
OSL	Operations and Science Lead
PCI	Potential Clinical Importance
PDMP	Protocol Deviation Management Plan
PP	Per Protocol
QC	Quality Control
RAP	Reporting & Analysis Plan
SAC	Statistical Analysis Complete
SDTM	Study Data Tabulation Model
SMQ	Standardised MedDRA Queries
SOP	Standard Operation Procedure
TA	Therapeutic Area
TFL	Tables, Figures & Listings

**9.6.2. Trademarks**

Trademarks of the GlaxoSmithKline Group of Companies	Trademarks not owned by the GlaxoSmithKline Group of Companies
None	Sas

## 9.7. Appendix 7: List of Data Displays

### 9.7.1. Data Display Numbering

The following numbering will be applied for RAP generated displays:

Section	Tables	Figures
Study Population	1.1 to 1.n	1.1 to 1.n
Safety	3.1 to 3.n	3.1 to 3.n
Section	Listings	
ICH Listings	1 to x	

### 9.7.2. Mock Example Shell Referencing

Non IDSL specifications will be referenced as indicated and if required example mock-up displays provided.

Section	Figure	Table	Listing
Study Population	POP_Fn	POP_Tn	POP_Ln
Safety	SAFE_Fn	SAFE_Tn	SAFE_Ln

**NOTES:**

- Non-Standard displays are indicated in the 'IDSL / Example Shell' or 'Programming Notes' column as '[Non-Standard] + Reference.'

### 9.7.3. Deliverables

Delivery [1]	Description
IA SAC	Interim Analysis SAC (as appropriate)
SAC	Final SAC

#### 9.7.4. Study Population Tables

Study Population Tables					
No.	Population	IDSL / Example Shell	Title	Programming Notes	Deliverable [Priority]
Subject Disposition					
1.1.	Safety	ES1	Summary of Subject Disposition	
 
MEA116841
 
201607
 
MEA116841 + 201607
 
	IA , SAC
1.2.	Safety	SD1	Summary of Treatment Status and Reasons for Discontinuation of Study Treatment	
 
MEA116841
 
201607
 
MEA116841 + 201607
 
	IA , SAC
1.3.	All Subjects Enrolled	NS1	Summary of Number of Participant by Country and Site ID	
 
MEA116841
 
201607
 
MEA116841 + 201607
 
	IA , SAC
Protocol Deviation					
1.4.	Safety	DV1	Summary of Important Protocol Deviations	
 
MEA116841
 
	IA , SAC
Population Analysed					
1.5.	All Subjects Enrolled	mid_mepo_egpa_lap /interim1 Table 1.1	Summary of Study Populations	
 
MEA116841
 
201607
 
MEA116841 + 201607
 
	IA , SAC
Demographic and Baseline Characteristics					
1.6.	Safety	DM1	Summary of Demographic Characteristics	
 
MEA116841
 
201607
 
MEA116841 + 201607
 
	IA , SAC

## CONFIDENTIAL

MEA116841

Study Population Tables					
No.	Population	IDSL / Example Shell	Title	Programming Notes	Deliverable [Priority]
1.7.	All Subjects Enrolled	DM11	Summary of Age Ranges	
 
MEA116841
 
201607
 
MEA116841 + 201607
 
	IA , SAC
1.8.	Safety	DM5	Summary of Race and Racial Combinations	
 
MEA116841
 
201607
 
MEA116841 + 201607
 
	IA , SAC
1.9.	Safety	mid_mepo_egpa_lap /interim1 Table 1.10	Summary of Race and Racial Combinations Details	
 
MEA116841
 
201607
 
MEA116841 + 201607
 
	IA , SAC
1.10.	Safety	mid_mepo_egpa_lap /interim1 Table 1.11	Summary of Cardiovascular Assessments – Screening Questions	
 
MEA116841
 
201607
 
MEA116841 + 201607
 
	IA , SAC
1.11.	Safety	mid_mepo_egpa_lap /interim1 Table 1.12	Summary of Cardiovascular Assessments – Family History	
 
MEA116841
 
201607
 
MEA116841 + 201607
 
	IA , SAC
1.12.	Safety	mid_mepo_egpa_lap /interim1 Table 1.13	Summary of Oral Corticosteroid Therapy Taken Before the Treatment Period	
 
MEA116841
 
201607
 
MEA116841 + 201607
 
	IA , SAC
1.13.	Safety	mid_mepo_egpa_lap /interim1 Table 1.14	Summary of Oral Corticosteroid Therapy Taken During the Treatment Period	
 
MEA116841
 
201607
 
MEA116841 + 201607
 
	IA , SAC

### 9.7.5. Safety Tables

Safety: Tables					
No.	Population	IDSL / Example Shell	Title	Programming Notes	Deliverable [Priority]
Exposure					
3.1.	Safety	mid_mepo_egpa_lap /interim1 Table 3.1	Summary of Exposure to Study Treatment	
 
MEA116841
 
201607
 
MEA116841 + 201607
 
	IA , SAC
3.2.	Safety	mid_mepo_egpa_lap /interim1 Table 3.2	Summary of Number of Treatment Administered	
 
MEA116841
 
201607
 
MEA116841 + 201607
 
	IA , SAC
Adverse Events (AEs)					
3.3.	Safety	AE1	Summary of On-Treatment Adverse Events by System Organ Class and Preferred Term	
 
MEA116841
 
201607
 
	IA , SAC
3.4.	Safety	AE1	Summary of Post-Treatment Adverse Events by System Organ Class and Preferred Term	
 
MEA116841
 
201607
 
	IA , SAC
3.5.	Safety	AE3	Summary of Common (>=3%) Adverse Events by Preferred Term	
 
MEA116841
 
201607
 
	IA , SAC
3.6.	Safety	AE1	Summary All Drug-Related Adverse Events by System Organ Class and Preferred Term	
 
MEA116841
 
201607As 3.1 notes
 
	IA , SAC
3.7.	Safety	AE3	Summary of Adverse Events Leading to Permanent Discontinuation of Study Treatment or Withdrawal from Study by Preferred Term	
 
MEA116841
 
201607For studies with few events/participants, listing is sufficient.
 
	IA , SAC

Safety: Tables					
No.	Population	IDSL / Example Shell	Title	Programming Notes	Deliverable [Priority]
3.8.	Safety	AE15	Summary of Common (>=3%) Non-serious Adverse Events by System Organ Class and Preferred Term (Number of Participant and Occurrences)	
 
MEA116841
 
201607Common' to be defined by study/project team. For studies with very few events/participants, listing is sufficient: discuss this option with your disclosure representative.
 
	IA , SAC
3.9.	Safety	AE5A	Summary of On-Treatment Adverse Events by System Organ Class and Preferred Term and Maximum Intensity	
 
MEA116841
 
201607Common' to be defined by study/project team. For studies with very few events/participants, listing is sufficient: discuss this option with your disclosure representative.
 
	IA , SAC
Serious and Other Significant Adverse Events					
3.10.	Safety	AE1	Summary of Pre-Treatment Serious Adverse Events by System Organ Class and Preferred Term	
 
MEA116841
 
201607For studies with few events/participants listing is sufficient: discuss this option with your disclosure representative.
 
MEA116841 + 201607
 
	IA , SAC

Safety: Tables					
No.	Population	IDSL / Example Shell	Title	Programming Notes	Deliverable [Priority]
3.11.	Safety	AE1	Summary of On-Treatment Serious Adverse Events by System Organ Class and Preferred Term	
 
MEA116841
 
201607For studies with few events/participants listing is sufficient: discuss this option with your disclosure representative.
 
MEA116841 + 201607
 
	IA , SAC
3.12.	Safety	AE1	Summary of Post-Treatment Serious Adverse Events by System Organ Class and Preferred Term	
 
MEA116841
 
201607For studies with few events/participants listing is sufficient: discuss this option with your disclosure representative.
 
MEA116841 + 201607
 
	IA , SAC
3.13.	Safety	AE16	Summary of Serious Adverse Events by System Organ Class and Preferred Term (Number of Participants and Occurrences)	Required for data disclosure 
 
MEA116841
 
201607For studies with few events/participants listing is sufficient: discuss this option with your disclosure representative.
 
MEA116841 + 201607
 
	IA , SAC

Safety: Tables					
No.	Population	IDSL / Example Shell	Title	Programming Notes	Deliverable [Priority]
3.14.	Safety	AE1	Summary of On-Treatment Non-Fatal Serious Adverse Events by System Organ Class and Preferred Term	
 
MEA116841
 
201607For studies with few events/participants listing is sufficient: discuss this option with your disclosure representative.
 
MEA116841 + 201607
 
	IA , SAC
3.15.	Safety	AE1	Summary of Fatal Serious Adverse Events by System Organ Class and Preferred Term	
 
MEA116841
 
201607For studies with few events/participants listing is sufficient: discuss this option with your disclosure representative.
 
MEA116841 + 201607
 
	IA , SAC
3.16.	Safety	AE1	Summary of Drug-Related Non-Fatal Serious Adverse Events by System Organ Class and Preferred Term	
 
MEA116841
 
201607For studies with few events/participants listing is sufficient: discuss this option with your disclosure representative.
 
MEA116841 + 201607
 
	IA , SAC

Safety: Tables					
No.	Population	IDSL / Example Shell	Title	Programming Notes	Deliverable [Priority]
3.17.	Safety	AE1	Summary of Drug-Related Fatal Adverse Events by System Organ Class and Preferred Term	
 
MEA116841
 
201607For studies with few events/participants listing is sufficient: discuss this option with your disclosure representative.
 
MEA116841 + 201607
 
	IA , SAC
3.18.	Safety	AE3	Summary of Non-Serious Drug-Related Adverse Events by Overall Frequency	
Required for Plain Language Summary
 
 
MEA116841
 
201607For studies with few events/participants listing is sufficient: discuss this option with your disclosure representative.
 
MEA116841 + 201607
 
	IA , SAC
3.19.	Safety	AE3	Summary of Serious Drug-Related Adverse Events by Overall Frequency	
Required for Plain Language Summary
 
 
MEA116841
 
201607For studies with few events/participants listing is sufficient: discuss this option with your disclosure representative.
 
MEA116841 + 201607
 
	IA , SAC

Safety: Tables					
No.	Population	IDSL / Example Shell	Title	Programming Notes	Deliverable [Priority]
3.20.	Safety	mid_mepo_egpa_lap /interim1 Table 3.16	Summary of All Cardiovascular Events Reported by the Investigator	
 
MEA116841
 
201607 For studies with few events/participants listing is sufficient: discuss this option with your disclosure representative.
 
MEA116841 + 201607
 
	IA , SAC
Adverse Events of Special Interest					
3.21.	Safety	mid_mepo_egpa_lap /interim1 Table 3.17	Summary of On-Treatment Adverse Events of Special Interest: Systemic Reactions	
 
MEA116841
 
201607
 
	IA , SAC
3.22.	Safety	mid_mepo_egpa_lap /interim1 Table 3.18	Summary of On-Treatment Adverse Events of Special Interest: Systemic Reactions, by Whether Related to Investigational Product	
 
MEA116841
 
201607
 
	IA , SAC
3.23.	Safety	mid_mepo_egpa_lap /interim1 Table 3.19	Summary of Systemic Reactions Experienced on Day of Dosing	
 
MEA116841
 
201607
 
	IA , SAC
3.24.	Safety	mid_mepo_egpa_lap /interim1 Table 3.20	Summary of On-Treatment Adverse Events of Special Interest: Systemic Hypersensitivity Reactions	
 
MEA116841
 
201607
 
	IA , SAC
3.25.	Safety	mid_mepo_egpa_lap /interim1 Table 3.21	Summary of On-Treatment Adverse Events of Special Interest: Systemic Non-Allergic Reactions	
 
MEA116841
 
201607
 
	IA , SAC

Safety: Tables					
No.	Population	IDSL / Example Shell	Title	Programming Notes	Deliverable [Priority]
3.26.	Safety	mid_mepo_egpa_lap /interim1 Table 3.22	Summary of On-Treatment Adverse Events of Special Interest: Local Injection Site Reactions	
 
• MEA116841
 
• 201607
 
	IA , SAC
3.27.	Safety	mid_mepo_egpa_lap /interim1 Table 3.23	Summary of On-Treatment Adverse Events of Special Interest: Local Injection Site Reactions, by Whether Related to Investigational Product	
 
• MEA116841
 
• 201607
 
	IA , SAC
3.28.	Safety	mid_mepo_egpa_lap /interim1 Table 3.24	Summary of On-Treatment Adverse Events of Special Interest: Systemic Reactions That According to Investigator Met Criteria for Anaphylaxis	
 
• MEA116841
 
• 201607
 
	IA , SAC
3.29.	Safety	mid_mepo_egpa_lap /interim1 Table 3.25	Summary of On-Treatment Adverse Events of Special Interest: Potential Opportunistic Infections	
 
• MEA116841
 
• 201607
 
	IA , SAC
3.30.	Safety	mid_mepo_egpa_lap /interim1 Table 3.26	Summary of On-Treatment Adverse Events of Special Interest: Malignancies	
 
• MEA116841
 
• 201607
 
	IA , SAC
3.31.	Safety	mid_mepo_egpa_lap /interim1 Table 3.27	Summary of On-Treatment Adverse Events of Special Interest: Serious Cardiac, Vascular and Thromboembolic	
 
• MEA116841
 
• 201607
 
	IA , SAC
3.32.	Safety	mid_mepo_egpa_lap /interim1 Table 3.28	Summary of On-Treatment Adverse Events of Special Interest by Cardiovascular History or Risk: Serious Cardiac, Vascular and Thromboembolic	
 
• MEA116841
 
• 201607
 
	IA , SAC
3.33.	Safety	mid_mepo_egpa_lap /interim1 Table 3.29	Summary of On-Treatment Adverse Events of Special Interest: Serious Ischemic Events	
 
• MEA116841
 
• 201607
 
	IA , SAC

Safety: Tables					
No.	Population	IDS / Example Shell	Title	Programming Notes	Deliverable [Priority]
3.34.	Safety	mid_mepo_egpa_lap /interim1 Table 3.30	Summary Profile of On-Treatment Adverse Events of Special Interest: Systemic Reactions	
 
• MEA116841
 
• 201607
 
	IA , SAC
3.35.	Safety	mid_mepo_egpa_lap /interim1 Table 3.31	Summary Profile of On-Treatment Adverse Events of Special Interest: Systemic Hypersensitivity Reactions	
 
• MEA116841
 
• 201607
 
	IA , SAC
3.36.	Safety	mid_mepo_egpa_lap /interim1 Table 3.32	Summary Profile of On-Treatment Adverse Events of Special Interest: Systemic Non-Allergic Reactions	
 
• MEA116841
 
• 201607
 
	IA , SAC
3.37.	Safety	mid_mepo_egpa_lap /interim1 Table 3.33	Summary Profile of On-Treatment Adverse Events of Special Interest: Local Injection Site Reactions	
 
• MEA116841
 
• 201607
 
	IA , SAC
3.38.	Safety	mid_mepo_egpa_lap /interim1 Table 3.34	Summary Profile of On-Treatment Adverse Events of Special Interest: Potential Opportunistic Infections	
 
• MEA116841
 
• 201607
 
	IA , SAC
3.39.	Safety	mid_mepo_egpa_lap /interim1 Table 3.35	Summary Profile of On-Treatment Adverse Events of Special Interest: Malignancies	
 
• MEA116841
 
• 201607
 
	IA , SAC
3.40.	Safety	mid_mepo_egpa_lap /interim1 Table 3.36	Summary Profile of On-Treatment Adverse Events of Special Interest: Serious Cardiac, Vascular and Thromboembolic	
 
• MEA116841
 
• 201607
 
	IA , SAC
3.41.	Safety	mid_mepo_egpa_lap /interim1 Table 3.37	Summary Profile of On-Treatment Adverse Events of Special Interest: Serious Ischemic Events	
 
• MEA116841
 
• 201607
 
	IA , SAC

Safety: Tables					
No.	Population	IDSL / Example Shell	Title	Programming Notes	Deliverable [Priority]
Exposure-Adjusted Adverse Events					
3.42.	Safety	mid_mepo_egpa_lap /interim1 Table 3.38	Summary of Exposure Adjusted On-Treatment Adverse Events	
 
• MEA116841
 
• 201607
 
	IA , SAC
3.43.	Safety	mid_mepo_egpa_lap /interim1 Table 3.39	Summary of Exposure Adjusted Most Frequent On-Treatment Adverse Events Reported by 3% or More Subjects In Any Treatment Group	
 
• MEA116841
 
• 201607
 
	IA , SAC
3.44.	Safety	mid_mepo_egpa_lap /interim1 Table 3.40	Summary of Exposure Adjusted Drug Related Adverse Events	
 
• MEA116841
 
• 201607
 
	IA , SAC
3.45.	Safety	mid_mepo_egpa_lap /interim1 Table 3.41	Summary of Exposure Adjusted On-Treatment Adverse Events Leading To Permanent Discontinuation of Study Drug or Withdrawal From Study	
 
• MEA116841
 
• 201607
 
	IA , SAC
3.46.	Safety	mid_mepo_egpa_lap /interim1 Table 3.42	Summary of Exposure Adjusted On-Treatment Serious Adverse Events	
 
• MEA116841
 
• 201607
 
	IA , SAC
3.47.	Safety	mid_mepo_egpa_lap /interim1 Table 3.43	Summary of On-Treatment Adverse Events by Age Category	
 
• MEA116841
 
• 201607
 
	IA , SAC
3.48.	Safety	mid_mepo_egpa_lap /interim1 Table 3.44	Summary of On-Treatment Adverse Events by Sex	
 
• MEA116841
 
• 201607
 
	IA , SAC
3.49.	Safety	mid_mepo_egpa_lap /interim1 Table 3.45	Summary of On-Treatment Adverse Events by Race	
 
• MEA116841
 
• 201607201607
 
	IA , SAC

